### **3 STUDY DESIGN**

**Design:** The overall goal of this proposal is to test the feasibility of implementing MBDC to guide subsequent evaluation of effectiveness of the MBDC intervention in a full-scale embedded pragmatic clinical trial (ePCT). This study will use a stepped wedge incomplete design with random assignment to accommodate continuous enrollment of participants and a rolling schedule of initiating MBDC courses. We aim to examine the effects of MBDC on depressive symptoms and burden in CPs of PLWD. CPs will be referred to MBDC from three healthcare settings and surrounding community partners. MBDC program registration and collection of administrative data will occur via Presence Care's web-based platform. MBDC courses will be taught in groups via web-based video calls by Presence Care certified instructors, including one by an African American trainee. Eight or more courses will be taught over 9 months. Upon registering, CPs will select two preferred days/times for class and will be randomized to one of them. Participants may not be assigned to the instructor at their memory clinic. With up to 15 participants anticipated per course, a total of up to 130 CPs will be enrolled. Administrative data will be collected at the time of registration, prior to the MBDC course, immediately following the MBDC course, and 3 months later (Figure 4). The

administrative data collected will be used as pragmatic outcomes in this study. Participants will be a part of the study for about 7 months including 8 weeks of intervention, a variable pre-intervention control period, and a 3-month follow-up period. We will request a waiver of informed consent for this study. We will also request a partial HIPAA waiver of authorization for use of electronic health record data for recruitment purposes. The administrative data collected by Presence Care is not protected health information; no HIPAA authorization/waiver is required, but the data obtained by the research team from Presence Care for research purposes will be covered by a data use agreement.

**Study population:** The study population consists of CPs of PLWD from three settings. Multiple strategies described below will be used to increase the diversity of CP participating in MBDC.

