**Figure 4. Study Design**

**Settings:** The three healthcare settings that will refer CPs to MBDC in this pilot include:

- the HealthPartners Center for Memory & Aging in St. Paul, MN;
- the Ray Dolby Brain Health Center at California Pacific Medical Center, a Sutter Health affiliate in San Francisco, CA; and
- the University of Michigan – Alzheimer’s Disease Research Center in Ann Arbor, MI.

Challenges to conducting ePCTs in CPs include the lack of pragmatically available clinical outcomes and the complexity of collecting and harmonizing data across multiple, diverse healthcare systems. MBDC evaluation data is currently being collected at the three pilot sites in different ways. To overcome these challenges, we will partner with Presence Care to develop and implement a permanent centralized process for MBDC class registration and administrative data collection on their website. This upgraded infrastructure will enable the collection of common administrative data, including questionnaires with clinical outcomes, for long-term use in evaluation of the program.

**Randomization scheme:** At the time of enrollment (registration on the Presence Care site), a CP will be presented with several currently enrolling class options (multiple days/times of week) and asked to select two that work with their schedule. They will then be randomly enrolled in one of the two selected courses, allowing for randomization on the class level while still accommodating the participant’s schedule. If a CP declines the assigned MBDC course, they will be allowed to self-select a course or to withdraw. As randomization is planned for the full-scale ePCT, it is important to determine acceptability of this component of implementation. This is balanced with the health care settings needs to support care partners experiencing stress.

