### 6.2.2 Enrollment, Baseline, and/or Randomization

#### Randomization

Four weeks before a course is scheduled to start, CPs will be randomized to attend one of the two indicated as preferred days/times. They will be contacted by email of their assignment or by phone if that was the mode of registration. If a CP declines the assigned MBDC course, they will be given the option to choose their preferred day and time. We are assessing the feasibility of randomization and do not want to withhold the MBDC program from those for whom this is not feasible.

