## **9 STATISTICAL CONSIDERATIONS**

### **9.1 General Design Issues**

#### **Design choice and rationale**

A stepped wedge trial design was chosen to ensure all participants had the opportunity to participate in the MBDC course. This trial design has each individual contribute control and intervention data, allowing for within participant comparisons. The stepped wedge trials also provides flexibility with rolling recruitment as opposed to the requirement to fill a class that starts on a particular date, which has been a barrier in other mindfulness trials. An adaptive randomization schematic was chosen to ensure that the classes fill up at a relatively similar rate, another pragmatic concern to consider before attempting a larger study. For the secondary aim, shorter versions of the validated scales used to assess efficacy were chosen to align with the pragmatic nature of this work, ensuring participants spend minimum amount of time possible providing clinical outcome data.

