### 9.2.1 Treatment Assignment Procedures

At the time of MBDC enrollment (registration on the Presence Care site), a CP will be presented with several currently enrolling class options (multiple days/times of week) and asked to select two that work with their schedule. Approximately 4 weeks prior to the course start date, they will then be randomly enrolled in one of the two selected courses, allowing for randomization on the class level while still accommodating the participant's schedule. An adaptive randomization schematic will be used to adjust the probability of class assignment based on CPs already enrolled in the trial. Since randomization is preferred in the full-scale ePCT, it is important to assess the feasibility of the acceptability of the random assignment in this pilot. Once a CP has registered for a MBDC course, there is variable delay period until there are enough people to fill the class. During this time, Presence Care will send regular emails updates to stay in contact. Once a class option is full, CPs will be notified, and the class will start. If a CP situation or schedule has changed and they decline the assigned course, they will have the option choose a preferred day and time so that we do not deny anyone access to this program.

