Analysis will utilize linear mixed-models with random effects to account for clustering of data within MBDC course section as well as repeated measures within CPs to estimate the intervention effect on depressive symptoms and care-giver burden (Equation 1). In a scaled up ePCT, we expect the unit of randomization to continue to be course section, which is reflected in our choice of random effects. The model structure will be based on a standard ANCOVA used to evaluate change that adjusts for the pre-intervention measurement of the outcome variable with the post-intervention measurement as the model outcome. Each CP will contribute a pair of data points for the control period (Pre: Q1, Post: Q2) and intervention period (Pre: Q2, Post: Q3) which requires our random effects structure to account for repeated measurements within CPs. If there is no difference in change in efficacy outcomes, we expect Q2-Q1 = Q3-Q2. Each model will include covariates to adjust for possible confounding associated with CP demographics and CP history (age, race/ethnicity, socioeconomic measures, and length of caregiving). While the relative time of measurement is considered (pre/post) our analysis does not adjust for time over the course of the study, as we hypothesize any treatment effect would be time-agnostic within the year-long pilot study time frame. When an ePCT with a longer timeline is considered, this assumption will have to be revisited. A brief assessment of self-compassion and mindfulness scales outcomes will be performed using the responses collected from the “research only” section of the questionnaires. These results will help better understand the possible mechanisms between the intervention and clinical outcome for future ePCTs. These items will be removed at the conclusion of the pilot to decrease participant burden. All analysis will be performed in SAS 9.4 and significance determined using a two-sided alpha of 0.05.

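### The efficacy contrast is a non-randomised within-participant comparison of waiting period and course, not a randomised stepped wedge, and Table 2A is computed for a design the plan does not use

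*Combined protocol and SAP*

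**What the plan says.** Section 3 declares the design: "This study will use a stepped wedge incomplete design with random assignment to accommodate continuous enrollment of participants". Section 9.1 gives the reason, which is access: "A stepped wedge trial design was chosen to ensure all participants had the opportunity to participate in the MBDC course".

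The allocation is described in Sections 3, 4.3, 6.2.2 and 9.2.1. A CP registers and picks two class options. "They will then be randomly enrolled in one of the two selected courses, allowing for randomization on the class level". On timing, Section 6.2.2 says "Four weeks before a course is scheduled to start, CPs will be randomized to attend one of the two indicated as preferred days/times", and Section 9.2.1 says "Once a class option is full, CPs will be notified, and the class will start". The allocation probabilities are not fixed: "An adaptive randomization schematic will be used to adjust the probability of class assignment based on CPs already enrolled in the trial". A CP who declines the assigned class may choose another.

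Section 9.5 (Aim 2) uses two changes per CP: Q1 to Q2 as control and Q2 to Q3 as intervention. It adjusts each for its starting value and states that study time is not adjusted for. It explains the course-level random effect by saying that in a scaled-up trial "we expect the unit of randomization to continue to be course section, which is reflected in our choice of random effects". Under Equation 1, time period 1 is control and time period 2 is intervention.

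Section 9.2 says that 120 CPs would allow detection of 3 points on the CES-D-10 (SD 4, ICC 0.10, 80% power, two-sided alpha 0.05). Table 2A gives 2.68, 2.99 and 2.86 for ICC 0, 0.1 and 0.3.

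**The concern.** A stepped wedge supports a causal reading because the time at which units cross from control to intervention is randomised and the analysis separates that crossing from the passage of time. Here the randomisation settles which of two classes a CP attends. It is not used to settle whether, or when, waiting gives way to the course.

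Section 3 states an aim to examine effects on depressive symptoms and burden, Section 9.1 states an efficacy hypothesis, and Section 9.5 tests at 0.05. A result reported under the label of a stepped wedge with random assignment would be credited with protection it does not have. If Table 2A rests on the same label, its detectable differences do not describe the analysis that will be run.

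**Working it through.** **1. What is randomised.**

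| Feature | Randomised stepped wedge | This plan |
|---|---|---|
| Unit randomised | Cluster (or person) to a crossover time | CP, to one of two self-chosen classes |
| What the arms receive | Control or intervention at a given time | The programme in both |
| What sets the crossover | Random sequence | Class schedule and filling |
| Time in the model | Period effects | None |

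**2. Separability under Equation 1.** Each CP contributes one control period and then one intervention period. The treatment indicator and the period indicator are the same column (correlation 1.00). An intercept, treatment and period give a design matrix of rank 2 for 3 parameters, so treatment cannot be separated from order. In an 8-step wedge the correlation is 0.65 and the effect can be estimated.

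**3. Reproducing Table 2A.** Section 9.2 does not state the calculation. Assume the standard Hussey-Hughes variance for a complete wedge: I = 8 courses, one crossing per step, T = 9 periods, fixed period effects, SD 4, and n = 120/(8 x 9) = 1.667 observations per course-period.

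Var = I s²(s² + T t²) / [(I U - W) s² + (U² + I T U - T W - I V) t²], with s² = (1 - ICC) x 16/n and t² = ICC x 16.

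U is the sum of the treatment indicators over all course-periods (36). W and V are the sums of squared period totals and squared course totals (204 each). So I U - W = 84, and the coefficient of t² is 1296 + 2592 - 1836 - 1632 = 420. The detectable difference is (1.960 + 0.842) x SE.

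- ICC 0: s² = 9.60, t² = 0. Var = 737.28/806.40 = 0.914, giving **2.68**.
- ICC 0.1: s² = 8.64, t² = 1.6. Var = 1592.52/1397.76 = 1.139, giving **2.99**.
- ICC 0.3: s² = 6.72, t² = 4.8. Var = 2683.70/2580.48 = 1.040, giving **2.86**.

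All three match. With 30 courses, 30 steps and N = 450 the same formula gives 1.316, 1.495 and 1.444, against the printed 1.32, 1.49 and 1.44. A two-group calculation with a design effect (60 per group) gives 2.05, 3.17 and 4.67, which does not match.

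**4. Bias when there is no true effect (illustration).** Assumptions not in the documents: correlation 0.6 between any two measurements, no covariates, and Q3 - Q2 as the intervention change. The slope of change on the starting value is then about -(1 - 0.6) = -0.4. The estimate is the gap in natural change minus (-0.4) times the difference in mean starting value (intervention minus control).

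- Q1 transiently 1 point high: 1 - (-0.4)(-1) = **+0.6**. For 2 and 3 points: +1.2 and +1.8.
- Drift of -0.1 point per week. Q2 to Q3 is 10 days + 8 weeks + 3 days = 69 days, or 9.9 weeks.
  - 4-week wait: the gap is -0.1 x (9.9 - 4) = -0.59, and the estimate is -0.59 - (-0.4)(-0.4) = **-0.75**.
  - 8-week wait: the gap is -0.19, and the estimate is -0.19 - (-0.4)(-0.8) = **-0.51**.

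Simulation (N = 120, ICC 0.1, starting-value adjustment with participant-clustered errors in place of the mixed model) agrees: +0.59, +1.20 and +1.75, with false-positive rates of about 27%, 71% and 95%; and -0.77 and -0.55, with rates of about 41% and 22%. Repeat runs moved these rates by a few percentage points. With neither disturbance the rate is about 5%. A fall in score is a benefit, so the first kind of bias hides an effect and the second mimics one.

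**5. Order of size for a replacement figure.** For the raw difference of changes (Q3 - 2Q2 + Q1) with equal correlation rho, the detectable difference is 2.802 x sqrt(6 x 16 x (1 - rho)/120). This gives 2.51, 2.10, 1.77 and 1.37 for rho = 0, 0.3, 0.5 and 0.7. It assumes no course-level variation in change, no dropout and no starting-value adjustment. It shows only that the planned analysis has a different detectable difference; greater nominal precision does not remove the bias.

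**The case against.** Much of the needed candour is already there. Section 9.1 says the comparison is within participant and justifies the wedge by access and rolling recruitment. Section 9.2 says the pilot is not formally powered for efficacy. Section 9.5 calls the efficacy analysis preliminary, plans to report the uneven control period, and says the lack of time adjustment must be revisited in a longer trial. The unit-of-randomisation sentence is about the future trial, and class-level randomisation can be read loosely as CPs being randomised to a class. All of this stands and limits the stakes. But none of it says that the contrast is non-randomised, and the word continue in that sentence carries the claim back to the pilot.

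A reader might go further in three ways that the documents do not support.

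- That no CP has any random element in crossover time. The two chosen classes could start on different dates, so some waiting time could be random. This is neither planned nor used in the analysis, but it is not excluded.
- That any difference in natural change passes one-for-one into the effect. This is true of the raw change summaries only. Under Equation 1 the starting-value adjustment can shrink or enlarge it, as step 4 shows.
- That the estimate is no evidence at all. A change-versus-change contrast cancels a constant trend over equal intervals. The intervals here are not equal, so the protection is partial, but the result is still weak, preliminary evidence.

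**Conclusion.** The point holds for the efficacy part. The plan's label and its implied unit of randomisation are properties that the efficacy contrast does not have. What will be estimated is a non-randomised within-participant difference between change over a lead-in wait and change over the course. It is exposed in either direction to transient elevation at registration, order effects and unequal intervals. The illustrative biases, about +0.6 to +1.8 and -0.5 to -0.75 against the plan's 3 points, rest on assumed disturbances and an assumed correlation of 0.6; they show sensitivity and do not forecast the result.

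That Table 2A comes from a complete wedge with period effects is an inference, since the method is not stated. It is a strong one, because a single set of settings reproduces both columns.

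It would be wrong to conclude that the pilot fails its purpose. The feasibility objectives and the progression criteria (attendance and diversity) do not use the effect estimate.

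**What to change.** In the Précis and Sections 3, 4.3, 9.1, 9.2.1 and 9.5:

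- Describe the efficacy part as a single-group comparison in which each CP's waiting period is the lead-in control, plus individual random allocation of class to test acceptability.
- Name the CP as the unit randomised in the pilot. If course section is intended for the larger trial, say so as a change.
- State that the effect estimate is non-randomised and preliminary, and limit claims about randomisation to feasibility.

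In Section 9.2, recompute Table 2A for the two-period within-participant model, stating the correlation assumed between measurements, or say that the table applies to a different design.

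Before recomputing, reconcile a separate inconsistency: Equation 1 defines the intervention change as Q3 - Q1, while the text of Section 9.5 uses Q3 - Q2.

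The cost is wording, one recomputation and a less favourable design claim. Nothing in the conduct of the study changes.

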## **7 SAFETY ASSESSMENTS**

### **7.1 Specification of Safety Parameters**

This pragmatic study has limited data available for safety parameters. We will monitor depressive symptoms and caregiver burden measured as part of the administrative data. If significant increases are observed between registration and the pre-course questionnaire, we will discuss whether the delay period is detrimental to CPs. If significant increases are observed between the pre and post course surveys (the opposite results than we expect), we will discuss whether MBDC implemented in this manner is either not effective or doing harm and make changes.

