**Table 3.**

	Counts for feasibility	Use in analysis
Participants contacted	N	Total number of targeted mailings Estimate of clinic flyer distribution using print rates
Participants who enroll and are randomized into MBDC course section	a	Recruitment rate: a/N
Participants who start MBDC course	b	Participation rate: b/N, compare to a/N
Participants who complete course (6/9 modules)	c	Completion rate: c/b, used as main progression criteria Overall successful enrollment rate: c/N
Number who complete each module in real-time – k = 1, ..., 9	d k	Module specific completion rate: d k /b

Number who complete each module as a make-up session – k = 1, ..., 9	$e_k$	Module specific make-up completion rate: $e_k/b$ Compare to $d_k/b$ to assess fidelity of make-up offerings
Number who complete each questionnaire – m = 1,2,3	$f_m$	Questionnaire specific response rate: $f_m/a$ and/or $f_m/b$ if $a \neq b$

**Aim 2 - Secondary Feasibility and Efficacy Analyses:** The completeness of the CED-D-10 and ZBI-6 outcomes will be quantified by calculating the rate of CPs that respond to all items on each scale (CES-D-10: 10 items, ZBI-6: 6 items) at each assessment. The rate of completion for both scales will be presented overall and stratified by questionnaire, site, and by CP demographics. As the current study design results in a non-uniform length of the control period, the weeks between Q1 and Q2 will be recorded and summarized for the sample to better understand how the design could scale to a larger ePCT. A preliminary efficacy analysis will utilize the total scores for the CES-D-10 (range: 0 to 30) and ZBI-6 (range: 0 to 24) calculated for all completed questionnaires. Both outcomes will be summarized at each questionnaire timepoint using means and/or medians, as appropriate. Change over the control (Q2-Q1) and intervention (Q3-Q2) periods will be calculated for each CP and summarized for the sample. Descriptive summaries will be provided for responses from CP who complete the 3-month follow-up questionnaire (Q4) within the 12-month study timeframe and before the final analytic dataset is defined. These responses will not be used in any of the formal inferential analyses.

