**Equation 1.**

$$Change_{itk} = \beta_0 + \delta X_{itk} + \omega Pre_{itk} + \beta X_i + \gamma_{0ik} + v_{0k} + \epsilon_{ik}$$

i = Participant Subscript, 1, ..., N

k = Cluster Subscript, 1, ..., K

t = time period, 1 = Control, 2 = Intervention

Changeitk = Change in efficacy outcome over period t

Preitk = Pre measurement from period t

For Control period: Pre = Q1, Change = Q2 - Q1

For Intervention period: Pre = Q2, Change = Q3 - Q1

xitk = Binary indicator for intervention for patient i in k at time t

Xi = Vector of covariates for participant i

$\beta_0$  = General intercept of the model

$\delta$  = Intervention effect (coefficient of xitk)

$\omega$  = Baseline measurement adjustment effect (coefficient of Preitk)

$\beta$  = Vector of coefficients associated with covariates in Xi

$\gamma_{0ik}$  = Participant-specific random intercept with mean zero and variance  $\sigma_{\gamma}^2$

$v_{0k}$  = Cluster-specific random intercept with mean zero and variance  $\sigma_v^2$

$\epsilon_{itk}$  = Random error with mean zero and variance  $\sigma_{\epsilon}^2$

**Aim 3 - Exploratory Feasibility Analysis:** To explore the feasibility of obtaining online consent for research access to CP healthcare utilization records. The number of CPs who agree to access for themselves or the PLWED on Questionnaire 3 will be counted. While we will not specifically collect utilization data, the number of CPs who agree will inform the feasibility of including healthcare utilization as an outcome in a full-scale ePCT. Any differences in CP demographics between enrollees who opt-in and those who opt-out will be assessed.

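### The Equation 1 legend defines the intervention-period change as Q3 - Q1 when the rest of the plan means Q3 - Q2; once corrected, delta still assumes equal untreated change given Pre in both periods

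*Combined protocol and SAP*

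**What the plan says.** Section 9.5, Aim 2, plans a mixed model in which each care partner (CP) supplies one row for the control period and one for the intervention period. The outcome is the change over the period. The predictors are the Pre score, an intervention indicator and participant covariates, with random intercepts for participant and course.

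The intervention-period change is defined in conflicting ways:
- Aim 2 text: "Change over the control (Q2-Q1) and intervention (Q3-Q2) periods will be calculated for each CP".
- Aim 2 text on the model: for the intervention period, Q2 is the Pre and Q3 the Post measurement.
- Equation 1 legend, general definition: Change is the change in the outcome over period t.
- Equation 1 legend, specific line: "For Intervention period: Pre = Q2, Change = Q3 - Q1".

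On time, the plan says "our analysis does not adjust for time over the course of the study, as we hypothesize any treatment effect would be time-agnostic", and adds "When an ePCT with a longer timeline is considered, this assumption will have to be revisited". Its null expectation is "If there is no difference in change in efficacy outcomes, we expect Q2-Q1 = Q3-Q2". Because the control period is not of uniform length, "the weeks between Q1 and Q2 will be recorded and summarized for the sample", but length does not enter the model.

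**The concern.** A programmer working from Equation 1 would build the outcome from its legend. With Pre = Q2, an outcome of Q3 - Q2 gives the same delta as an ANCOVA on Q3. Q3 - Q1 does not, because it adds the waiting-period change to the intervention row when that change is already the control row's outcome.

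The second issue is what delta means once the legend is right. Control always precedes intervention, and randomisation only chooses between two class slots (Sections 3 and 9.2.1). The covariates and random intercepts are constant across a participant's two rows, so they cannot absorb a difference between periods. A treatment effect that is constant over the study year is one assumption. Equal untreated change in two successive periods of different length is another, and only the first is argued. At stake is how the preliminary delta and its 0.05-level test are read, including as guidance for the full-scale trial.

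**Working it through.** The plan gives no figure for this bias, so there is none to reproduce.

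**Algebra.** Let m1 and m2 be the mean changes over Q1-Q2 and Q2-Q3, and omega the Pre coefficient. The mean Pre score differs between rows by m1. In a least-squares fit:
- Q3 - Q2: delta = m2 - m1 - omega x m1 = m2 - (1 + omega) x m1.
- Q3 - Q1: delta = (m1 + m2) - m1 - omega' x m1 = m2 - omega' x m1.

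Under the plan's own null, m1 = m2 = c, the corrected model gives delta = -omega x c. That is zero only if c = 0. If m1 = 0, both versions return m2.

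**Period lengths.** Q2 is sent 10 days before the course and Q3 3 days after it (Section 6.1). With 8 weeks of intervention (Section 3), Q2 to Q3 is L = (10 + 56 + 3)/7 = 9.86 weeks by send dates. If answers come at the reminders, it ranges from (1 + 56 + 3)/7 = 8.6 to (10 + 56 + 18)/7 = 12.0 weeks. The wait W from Q1 to Q2 varies. Participation of about 7 months (30.4 weeks), less 13 weeks of follow-up, 8 weeks of course and 1.4 weeks, leaves a mean of about 8.0 weeks. For 6.5 to 7.5 months the mean is 5.8 to 10.1 weeks.

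**Assumed values.** The documents give neither the within-participant correlation r nor an untreated drift d in points per week. For equal variances omega is about -(1 - r), and omega' about -(1 - r)/2. With steady drift and no MBDC effect:
- Q3 - Q2: bias = d(L - rW) = d(L - W) [unequal length] + d(1 - r)W [Pre term].
- Q3 - Q1: bias = d(L + (1 - r)W/2).

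At d = 0.1, r = 0.6, W = 8:
- Q3 - Q2: 0.1 x (9.86 - 4.8) = 0.51, of which length is 0.19 and the Pre term 0.32.
- Q3 - Q1: 0.1 x (9.86 + 1.6) = 1.15.

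**Simulation.** 1,500 trials per case; 8 courses of 15, SD 4 and course ICC 0.10 (as in Section 9.2); r = 0.6; mean wait 8 weeks; complete data; no demographic covariates; REML with participant and course intercepts.

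| Drift per week | Bias, Q3 - Q2 | Bias, Q3 - Q1 |
|---|---|---|
| 0 | 0 | 0 |
| 0.02 | 0.10 | 0.25 |
| 0.05 | 0.24 | 0.61 |
| 0.1 | 0.52 | 1.24 |

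Drift of 0.1 is a stress case: 5.2 points a year, or 1.3 SD.

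Range for Q3 - Q2 at drift 0.1:
- 0.65 at a 6-week and 0.42 at a 10-week mean wait.
- 0.69 for r = 0.4 and 0.37 for r = 0.8 (8 weeks).
- With both periods fixed at 9.86 weeks, 0.43 with Pre and 0.01 without it, so equal lengths alone do not remove the bias.

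**Direction.** Drift of -0.1 gives -0.54. The bias takes the sign of a steady drift until W reaches 9.86/0.6 = 16.4 weeks. In a smaller run (150 trials) with a true effect of -3 and an assumed 2-point distress at registration decaying with a 6-week half-life, Q3 - Q2 gave -3.04 and Q3 - Q1 gave -3.99.

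**The case against.** Three statements agree on Q3 - Q2 and one line differs, so the intended analysis is not in real doubt. That stands as a reading of intent, and a reader should not infer that the sponsor means to analyse Q3 - Q1. The line is still in the specification that would be programmed, it changes the estimate, and correcting it is free.

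The time assumption is largely disclosed: the plan says that time is omitted, writes down the equal-change null, acknowledges the uneven control period and defers the matter to a longer trial. This mostly stands. What is missing is that equal raw change is not the null of a model containing Pre.

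The sizes rest on assumed drift and correlation. That stands too. At drifts of 0.02 and 0.05 the corrected model's bias is 0.10 and 0.24, against a standard error of about 0.46.

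A reader might infer that the design manufactures a benefit. The documents do not support that. MBDC is expected to lower scores, so worsening during the study pushes delta upward and hides benefit; only sustained improvement flatters MBDC. Section 7.1 says "If significant increases are observed between registration and the pre-course questionnaire, we will discuss whether the delay period is detrimental to CPs", but that is a conditional safety provision about increases, not a forecast.

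A reader might also conclude that a time-adjusted model of the scores should replace Equation 1. For an assumed 1-point fall soon after registration (3-week time constant), that model's bias was 0.58 against 0.40 for the planned model. It is a reasonable optional addition, not a required replacement.

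**Conclusion.** The legend line is wrong as written and should be corrected before analysis. Followed literally, it more than doubles the bias under the assumed steady drift with an 8-week wait (about 1.1 to 1.2 points against about 0.5 at 0.1 point a week), and it makes delta something other than the ANCOVA effect on Q3.

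The equal-untreated-change assumption is a real but smaller point. It calls for a clear statement and a supporting analysis, not a new primary model. The documents cannot say whether untreated change occurs, in which direction or how fast; with none, the corrected delta is unbiased.

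The stakes are minor to moderate. Section 9.2 says the pilot is not formally powered for efficacy, Section 9.5 calls the analysis preliminary, and the progression criteria in Section 9.1 rest on attendance and on the representativeness of recruitment.

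**What to change.** 1. In the Equation 1 legend, change the intervention-period definition to Change = Q3 - Q2. This costs nothing.

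2. Beside the planned estimate, report the same mixed model without the Pre term. Its null is the plan's own, Q2-Q1 = Q3-Q2. In least-squares terms the two estimates differ by omega x m1, so the gap shows how much the Pre term contributes. Let the covariance of a participant's two changes be negative, because they share Q2 with opposite signs. Treating them as uncorrelated uses variance 4s² for the difference in changes when Q3 - 2Q2 + Q1 has variance 6s² (s² = within-participant residual variance). That would shrink the standard error by a factor of √(4/6) = 0.82.

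3. Show Q2 - Q1 against weeks waited, using the registration and questionnaire dates that REDCap already records.

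4. State that delta is interpreted as conditional on equal expected untreated change, given Pre, in both periods.

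The cost is a little more analysis and no new data. The model without Pre corrects neither unequal period lengths nor nonlinear change. Under steady drift its bias is d(L - W), which at r = 0.6 is larger in absolute size than the planned model's once the mean wait exceeds 2 x 9.86/1.6 = 12.3 weeks. It therefore belongs beside the planned estimate, not in its place.
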